10.2 Serious Adverse Events

A serious adverse event (SAE) is defined as any untoward medical occurrence that at any dose:

1. Results in death.
2. Is immediately life-threatening (ie, in the opinion of the Investigator, the AE places the subject at immediate risk of death; it does not include a reaction that, had it occurred in a more severe form, might have caused death).
3. Requires inpatient hospitalization or results in prolongation of an existing hospitalization.
4. Results in persistent or significant disability or incapacity. (Note: The term "disability" refers to events that result in a substantial disruption of a subject's ability to conduct normal life function.)
5. Is a congenital anomaly or birth defect.
6. Is an important medical event (Note: The term "important medical event" refers to an event that, based upon appropriate medical judgment, may not be immediately life-threatening or result in death or hospitalization, but may jeopardize the subject or require intervention to prevent one of the other serious outcomes listed under the definition of SAE. Examples of important medical events include intensive treatment in an emergency room or at home for allergic bronchospasm; blood dyscrasias, or convulsions that do not result in hospitalization; or development of product dependency or product abuse.)

SAEs and/or follow up to SAEs including death due to any cause other than progression of the cancer under study, that occurs from the date of the first dose of study drug through 30 days following the last

dose of study drug, whether or not related to study drug(s), must be recorded on the CRF and must be reported within 2 business days supporting companies. External sites should report SAEs to the Duke study team within 24 hours. Reporting instructions for external sites can be found in the REDCap study eManual.

All SAEs must be followed until resolution, return to baseline condition, or stabilization. Any SAEs that are ongoing at the time the clinical database is closed will be reported to supporting companies as unresolved.

The initial report for each SAE or death should include at minimum the following information:

- protocol number and title
- patient initials, study identification number, sex, age
- date the event occurred
- description of the event
- seriousness criteria
- event causality or causal relationship
- study drug name(s)
- dose level and cycle number at the time the event occurred
- description of the patient's condition
- study status of patient at time of report
- responsible investigator name and contact details

The Investigator should report a diagnosis or a syndrome rather than individual signs or symptoms. The Investigator should also try to separate a primary AE considered as the foremost untoward medical occurrence from secondary AEs which occurred as complications. Whenever possible, the Investigator should also provide the batch or lot number of the study drug(s).

SAE Reporting Procedure:

Immediately upon awareness of a SAE, the Investigator (or designee) completes the **DCI SAE Report Form** and will submit the form within 2 business days of knowledge of the event to the funding company. External sites should submit the form within 24 hours to the Duke study team via the REDCap SAE reporting tool. In accordance with applicable regulations, Investigators must report SAEs to their local IRB according to their institutional guidelines.

Note: It is imperative that initial SAE reports are submitted as soon as possible (within 2 business days of knowledge of the event) with available information to the supporting company. Missing and/or clarified event information may be provided in a follow-up report.

Follow-up information including severity, action taken, concomitant medications, and outcome should be communicated to the funding company as soon as possible using the same forms mentioned above.

:

The Lead PI will review the report form with accompanying source document, sign page 5, and then the PI or designee will promptly submit it to the supporting company.

If the event meets the Duke University Health System (DUHS) IRB reporting requirements, the Duke GI Oncology regulatory coordinator will submit information about the SAE including the Lead PI's

assessment as a safety event to the DUHS IRB within 5 business days. Any study-related death must be reported to the IRB within 24 hours of discovery.

Within two business days of receipt, the Duke study team will also submit the SAE report form and other relevant safety information to the following supporting companies:

Merck Global Safety
ATTN: Worldwide Product Safety
[contact]

Expedited Reporting Procedure for Duke Cancer Institute (Coordinating Center):

Duke Cancer Institute as the coordinating center for this study is responsible for reporting SAEs to the FDA in accordance with [21CFR 312.32](#). Any SAE that is possibly related and unexpected must be submitted to the FDA attached to the IND. If the SAE meets criteria for reporting to the FDA, the Duke study team will complete the Form FDA 3500A (MedWatch) and send to the Lead PI and the supporting companies that are noted above. This submission of the Form FDA 3500A to the FDA attached to the IND will be completed by the Duke GI Oncology Clinical Trials Regulatory Coordinator.

- All unexpected, drug related SAEs that are fatal or life-threatening will be reported to the FDA by phone or fax within 7 calendar days of initial receipt of the information and will provide a complete report within 8 days of the initial report submission (by calendar day 15).
- All unexpected, treatment-related SAEs that are not fatal or life-threatening will be reported in a written report to the FDA within 15 days of initial receipt of the information.

The Duke study team will forward all expedited reports to all participating investigators in the form of an Investigator Alert. The Investigator Alert template is available on the DCI intranet titled “Safety Reporting for Multi-site IITs Notification Email”.

10.3 Events of Clinical Interest

Select (non-serious and serious) adverse events called Events of Clinical Interest (ECI) that occur from the date of the first dose of study drug through 30 days following the last dose of study drug, must be recorded on the CRF and must be reported within 2 working days to Merck Global Safety.

An ECI for this study is any hepatic toxicity that is \geq Grade 2 or any grade resulting in dose modification or use of systemic steroids to the adverse event. Such adverse events include but are not limited to; hepatitis, autoimmune hepatitis, and transaminase elevations (ALT and/or AST).

Any overdose of pembrolizumab (1,000 mg or greater) is also considered an ECI for this study and should be reported as such, regardless of the outcome.

ECI Reporting Procedure:

Immediately upon awareness of an ECI, the Investigator (or designee) completes the **DCI SAE Report Form** and will submit the form within 2 business days of knowledge of the event to the funding company. External sites should submit the form within 24 hours to the Duke study team via the REDCap SAE reporting tool.

Note: It is imperative that initial ECI reports are submitted as soon as possible (within 2 business days of knowledge of the event) with available information to the supporting company. Missing and/or clarified event information may be provided in a follow-up report.

Follow-up information including severity, action taken, concomitant medications, and outcome should be communicated to the funding company as soon as possible using the same form mentioned above.

The Lead PI will review the report form with accompanying source document, sign page 5, and the PI or designee will then promptly submit it to the funding company.

Within two business days of receipt, the study team will also submit the SAE report form and other relevant safety information to the following supporting company:

Merck Global Safety
ATTN: Worldwide Product Safety
[contact]

10.4 Other Safety Considerations

The Investigator must also report in the same timelines as SAEs any incidence of medication error, occupational exposure, abuse or misuse that is associated with or result in an adverse event. All related fatal outcomes must also be reported in the same timeline as a SAE.

Refer to SAE reporting procedures in [Section 10.2](#).

10.4.1 Pregnancy and Lactation

Although pregnancy and lactation are not considered adverse events, it is the responsibility of Investigator or designee to report any pregnancy or lactation in a subject (spontaneously reported to them), including the pregnancy of a male subject's female partner that occurs during the trial or within 120 days of following cessation of treatment. All subjects and female partners of male subjects who become pregnant must be followed to the completion/termination of the pregnancy. Pregnancy outcomes of spontaneous abortion, missed abortion, benign hydatidiform mole, blighted ovum, fetal death, intrauterine death, miscarriage and stillbirth must be reported as serious events (important medical events). If the pregnancy continues to term, the outcome (health of infant) must also be reported.

Such events must be reported reported in the same procedure as an SAE. Refer to SAE reporting procedures in [Section 10.2](#).

10.4.2 Medication Overdose and Error

For purposes of this trial, an overdose of pembrolizumab will be defined as any dose of 1,000 mg or greater (≥ 5 times the indicated dose) and is an event of clinical interest (see Section 10.3 for reporting instructions). No specific information is available on the treatment of overdose of pembrolizumab. Appropriate supportive treatment should be provided if clinically indicated. In the event of overdose, the subject should be observed closely for signs of toxicity. Monitoring should be based upon good medical judgment, taking into account the level of overdose, evolving toxicities, and other relevant medical and social factors specific to the patient. Appropriate supportive treatment should be provided if clinically indicated.

If an adverse event(s) is associated with ("results from") the overdose of study drug(s), the adverse event(s) is reported as a SAE, even if no other seriousness criteria are met. Refer to SAE reporting procedures in [Section 10.2](#).

If a dose of pembrolizumab meeting the protocol definition of overdose is taken without any associated clinical symptoms or abnormal laboratory results, the overdose is reported as an ECI, using the terminology “accidental or intentional overdose without adverse effect.” Refer to ECI reporting procedures in [Section 10.3](#).

11.0 ADMINISTRATIVE RESPONSIBILITIES

11.1 Institutional Review Board/Independent Ethics Committee

Before study initiation, the Investigator must have written and dated approval/favorable opinion from the Institutional Review Board/Independent Ethics Committee (IRB/IEC) for the protocol, consent form, subject recruitment materials/process (e.g., advertisements), and any other written information to be provided to subjects.

The Investigator should provide the IRB/IEC with reports, updates, and other information (e.g., Safety Updates, Amendment IRB/IECs, and Administrative Letters) according to regulatory requirements and institution procedures.

Copies of all IRB/IEC approvals, as well as annual re-approvals and approved/stamped informed consent forms must be submitted to Duke GI Oncology Clinical Trials Office.

11.2 Protocol and Protocol Revisions

All revisions to the protocol will be provided to the supporting companies by the Lead PI or designee(s) at the Duke GI Oncology Clinical Trials Office. The Lead PI must have written and dated approval/favorable opinion from the Duke University Health System (DUHS) IRB of revised protocol prior to distribution to Investigators at external participating sites.

Investigators must obtain written and dated and approval/favorable opinion from the IRB/IEC before conducting any updated protocol version. Study must be conducted as described in the approved protocol. The Investigator must not implement changes of the approved protocol without prior written agreement by the Lead PI and prior review and documented approval/favorable agreement by the IRB/IEC of an amendment, except where necessary to eliminate an immediate hazard(s) to study subjects, or when the changes involve only logistical or administrative aspects of the study (e.g., changes in research personnel or change in phone numbers).

Documentation of approval(s) from the IRB/IEC must be sent to Duke GI Oncology Clinical Trials Office.

11.3 Protocol Deviations and Violations

A protocol deviation is non-adherence to protocol specific study procedures or schedules that does not involve inclusion/exclusion criteria, primary objective evaluation criteria, and/or Good Clinical Practice (GCP) guidelines.

A protocol violation is any significant divergence from the protocol such as non-adherence on the part of the subject, the Investigator, or the sponsor to protocol specific inclusion/exclusion criteria, primary objective evaluation criteria, and/or GCP guidelines.

As a matter of policy, the Lead PI (ie. sponsor) will not grant exceptions to protocol specific entry criteria to allow subjects to enter a study. If it is found that a subject who did not meet protocol eligibility criteria was entered in a study (a protocol violation), the Lead PI and/or designee(s) at the Duke GI Oncology Clinical Trials Office must be informed immediately. Such subjects will be discontinued from the study,

except in an exceptional instance following review and written approval by the Lead PI and the responsible IRB/IEC.

Protocol deviations and violations must be documented and reported to the Lead PI and/or designee(s) at the Duke GI Oncology Clinical Trials Office.

In accordance with applicable regulations, Investigators must report protocol deviations and violations to their local IRB/IEC according to their institutional guidelines.

11.4 Informed Consent

The Investigator must ensure that subjects or their legally acceptable representatives are clearly and fully informed about the purpose, potential risks and other critical issues regarding clinical trials in which they volunteer to participate. Preparation of the consent form is the responsibility of the Investigator and must include all elements required by CFR 21 Part 50.25 and their IRB. A copy of the proposed informed consent document must be submitted to the Lead PI or designee(s) at the Duke GI Oncology Clinical Trials Office for review and comment prior to submission to the local IRB/IEC.

Informed consent must be obtained prior to performing any study-related procedures that are not part of normal subject care, including screening and changes in medications. A copy of the signed informed consent form must be given to the study subject.

11.5 Source and Study Documentation

Source documents include all original recordings of observations or notations of clinical activities and all reports and records necessary for the evaluation and reconstruction of the clinical study. Accordingly, source documents include, but are not limited to, laboratory reports (including normal and abnormal results), radiology reports, subject diaries, biopsy reports, ultrasound photographs, subject progress notes, hospital charts or pharmacy records and any other similar reports or records of any procedure performed in accordance with the protocol.

Whenever possible, the original recording of an observation should be retained as the source document; however, a photocopy is acceptable provided that it is a clear, legible, and exact duplication of the original certified document.

When clinical observations are entered directly into an electronic medical record system (i.e. in lieu of original hardcopy records), the electronic record can serve as the source document if the system has must be validated to meet the FDA requirements for electronic records and signatures (i.e. meets [21 CFR Part 11](#) compliant).

Regulations require that Investigators maintain information in the study subject's medical records which corroborate data recorded on the CRF. In order to comply with these regulatory requirements, the following information will be maintained and made available as required by the Lead PI or designee(s), monitors, and/or regulatory inspectors:

- Medical history/physical condition of the study subject prior to involvement in the study sufficient to verify protocol entry criteria.
- Dated note that informed consent was obtained for the subject's participation in the study.
- Dated and signed notes for each subject visit including results of examinations.
- Notations on abnormal lab results and their resolution.
- Dated reports of special assessments (e.g., ECG reports).

- Dated and signed notes regarding adverse events (including event description, severity, onset date, duration, relation to study treatment, outcome and treatment for adverse event).
- Dated notes regarding concomitant medications taken during the study (including start and stop dates).
- Subject condition upon completion of or withdrawal from the study.

Study documentation includes all CRFs, data correction forms, source documents, monitoring logs and appointment schedules, sponsor-investigator correspondence and regulatory documents (e.g., protocol and amendments, IRB/IEC correspondence and approvals, approved and signed subject consent forms, Statement of Investigator form, and clinical study supplies receipts and distribution records).

The Investigator will prepare and maintain complete and accurate study documentation in compliance with GCP guidelines and applicable federal, state, and local laws, rules and regulations; and, for each subject participating in the study, promptly complete all CRFs and such other reports as required by this protocol following completion or termination of the clinical study or as otherwise required pursuant to any agreement with the Lead PI and Duke Cancer Institute (DCI).

The Investigator acknowledges that, within legal and regulatory restrictions and institutional and ethical considerations, study documentation will be promptly and fully disclosed to Lead PI or designee(s) by the Investigator upon request and also shall be made available at the Investigator's site upon request for inspection, copying, review and audit at reasonable times by representatives of the Lead PI and DCI or responsible government agencies as required by law.

The Investigator agrees to promptly take any reasonable steps that are requested by the Lead PI or designee(s) as a result of an audit to cure deficiencies in the study documentation and case report forms.

11.6 Case Report Forms

Subject data will be entered (ie. CRFs completed) into an electronic data capture (EDC) system called Medidata RAVE. This database is maintained on a secure Duke University server and is accessible via internet with login and password.

CRFs should be completed by trained study personnel according to guidelines provided by the Lead PI or designee(s) at the Duke GI Oncology Clinical Trials Office. The Investigator or qualified designee is responsible for recording and verifying the accuracy of subject data. The Investigator acknowledges that his/her electronic signature is the legally binding equivalent of a written signature. By entering his/her electronic signature, the Investigator confirms that all recorded data have been verified as accurate.

In the event of discrepant data, the study monitor or study designee will request data clarification from the Investigator or designee for which may be resolved electronically in the EDC system.

Accurate and reliable data collection will be ensured through verification and crosscheck of the CRFs against the Investigator's study records (source document verification) by the study monitor or study designee.

11.7 Monitoring and Audits/Inspections

The study will be monitored both internally by the Lead PI and externally by the Duke Cancer Institute (DCI) Monitoring Team in accordance with their NCI-approved "Institutional Protocol Monitoring Procedures and Guidelines for NIH-sponsored Research Involving Human Subjects".

In terms of internal review, the Lead PI and/or designee(s) will continuously monitor and tabulate adverse events. Appropriate reporting to the DUHS IRB will be made. If an unexpected frequency of Grade 3 or 4 adverse events occurs, depending on their nature, action appropriate to the nature and frequency of these adverse events will be taken. This may require a protocol amendment, dose escalation, or potentially closure of the study. The Lead PI of this study will also continuously monitor the conduct, data, and safety of this study to ensure that:

- Interim analyses occur as scheduled (if applicable);
- Stopping rules for toxicity and/or response are met;
- Risk/benefit ratio is not altered to the detriment of the subjects;
- Appropriate internal monitoring of adverse events and outcomes is done;
- Over-accrual does not occur;
- Under-accrual is addressed with appropriate amendments or actions;
- Data are being appropriately recorded on the CRF in a reasonably timely manner.

The Duke Cancer Institute (DCI) Monitoring Team will conduct monitoring visits to ensure subject safety and to ensure that the protocol is conducted, recorded, and reported in accordance with the protocol, standard operating procedures, GCP, and applicable regulatory requirements. As specified in the DCI Data and Safety Monitoring Plan, the DCI Monitoring Team will conduct routine monitoring after the third subject is enrolled, followed by annual monitoring of 1-3 subjects until the study is closed to enrollment and subjects are no longer receiving study interventions that are more than minimal risk.

An external site monitoring plan addendum describes monitoring at participating sites.

Additional monitoring may be prompted by findings from monitoring visits, unexpected frequency of serious and/or unexpected toxicities, or other concerns and may be initiated upon request of DUHS and DCI leadership, the DCI Cancer Protocol Committee, the Safety Oversight Committee (SOC), the sponsor, the Principal Investigator, or the IRB. All study documents must be made available upon request to the DCI Monitoring Team and other authorized regulatory authorities, including but not limited to the National Institute of Health, National Cancer Institute, and the FDA. Every reasonable effort will be made to maintain confidentiality during study monitoring.

The DCI Safety Oversight Committee (SOC) will perform annual reviews on findings from the DCI Monitoring Team visit and additional safety and toxicity data submitted by the Principal Investigator.

DCI Quality Assurance personnel, or designee, may conduct audits at sites. Audits will include, but not be limited to: audit trail of data handling and processes, SOPs, drug supply, presence of required documents, the informed consent process, and comparison of case report forms/database with source documents. The Investigator agrees to accommodate and participate in audits conducted at a reasonable time in a reasonable manner, as needed.

Regulatory authorities may also audit an Investigator during or after the study. The Investigator should contact the Lead PI and designee(s) at the Duke GI Oncology Clinical Trials Office as well as their local IRB, immediately if this occurs, and must fully cooperate with governmental (e.g., FDA) audits conducted at a reasonable time in a reasonable manner.

The Duke University Compliance Program - Human Subject Research Compliance (HSRC) section may conduct confidential audits to evaluate compliance with the protocol and the principles of GCP. The

Lead PI agrees to allow the HSRC auditor(s) direct access to all relevant documents and to allocate his/her time and the time of the study team at the Duke GI Oncology Clinical Trials Office to the CTQA auditor(s) in order to discuss findings and any relevant issues.

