2. To explore other changes in tissue and blood based biomarkers and their correlation with clinical outcomes.
3. To explore changes in immune cells and biomarkers in those who completed treatment and remain in complete response.

Patient Population

Histologically and/or cytologically documented and radiographically measurable (by RECIST 1.1) adenocarcinoma of the esophagus or stomach (HER2 negative) that is metastatic/recurrent and not amenable to potentially curative treatment (e.g., inoperable metastatic or locally recurrent disease). HER2 positive patients would be considered eligible only if there is a contraindication to Herceptin.

Study Design

The study will be conducted in two stages: 1) safety validation and 2) dose expansion.

1. Safety Validation Cohort: The first portion of the study will preliminarily establish the tolerability of the combination of pembrolizumab, oxaliplatin and capecitabine. Five (5) patients will be enrolled and their safety data after 21 days of treatment will be reviewed before additional patients are enrolled. Subjects on this portion of the study will only be enrolled at the Duke Cancer Institute.

2. Dose Expansion Cohort: The second portion of the study (ie. phase II) will enroll 30 patients. In the dose expansion cohort, the first cycle will be modified to allow one week of pembrolizumab monotherapy before starting capecitabine and oxaliplatin (XELOX) chemotherapy, which will allow analysis of biomarkers related to pembrolizumab. Subjects on this portion of the study will be enrolled at the Duke Cancer Institute and select external collaborating institutions.

Number of Subjects

In the Safety Validation Cohort, 5 evaluable subjects will be enrolled.

In the Dose Expansion Cohort, 30 evaluable subjects will be enrolled.

A total of 35 evaluable subjects will be accrued to this study to assess the efficacy, safety and tolerability of the combination of pembrolizumab, oxaliplatin and capecitabine.

Estimated Length of Study Participation

Estimated duration of subject enrollment is 12 months.

Patients will continue to receive study treatment until they experience unacceptable drug-related toxicity or disease progression. The maximum duration of treatment for pembrolizumab will be up to two years. The duration of treatment for XELOX will be until unacceptable drug-related toxicity or disease progression.

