3.3 Dose Expansion Cohort

Once 5 evaluable subjects have been treated in the safety validation cohort with no more than one occurrence of DLT as defined in Section 3.2.1, the second portion of the study (ie. phase II) will accrue

30 evaluable patients to assess the safety, tolerability, and efficacy of the RPTD of the combination of pembrolizumab, oxaliplatin and capecitabine in patients with previously untreated metastatic esophagogastric adenocarcinoma. Subjects on this portion of the study will be enrolled at the Duke Cancer Institute and select external collaborating institutions.

In the dose expansion cohort, the first cycle will be modified to allow one week of pembrolizumab monotherapy before starting XELOX chemotherapy, which will allow analysis of biomarkers related to pembrolizumab; thus Cycle 1 for the dose expansion cohort will be 4 weeks.

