- NOTE:** After Cycle 1, the treating physician may choose to hold oxaliplatin and continue capecitabine and pembrolizumab at current dose as clinically indicated. If toxicity resolves to grade 1 or less the treating physician may choose to restart oxaliplatin later in the patient's treatment course, the dose of oxaliplatin at which the patient restarts should be one dose level lower than last dose level on which patient was treated. The specific treatment approach used and dose modifications that occur are required to be reported in the Case Report Forms.

If grade 2 intolerable, grade 3 or grade 4 neurological toxicity (see Table 3E) is evident at the time of the next planned administration of oxaliplatin, then oxaliplatin administration will be held until the next treatment cycle. Capecitabine and pembrolizumab will be administered if otherwise appropriate.

Missed doses will not be made up. If toxicity resolves to grade 1 or less at next treatment cycle, resume oxaliplatin per instructions provided in Table 3E. If neurological toxicity is still present and has not resolved to grade 1 or less at the next treatment cycle, oxaliplatin will continue to be held. Patients may continue to receive capecitabine and pembrolizumab on study if otherwise appropriate.

Oxaliplatin may be repeatedly temporarily discontinued and then re-initiated in this fashion unless the patient has disease progression, whereby the patient will be removed from the study. However, if the patient is not receiving oxaliplatin at the time of progression, if it is appropriate and safe as determined by the treating physician that oxaliplatin can be restarted, oxaliplatin may be restarted and the patient may continue on treatment. If the patient has disease progression on oxaliplatin or it is not safe or appropriate to restart oxaliplatin, the patient will be removed from the study.

Dose escalations of oxaliplatin are not permitted at any time.

Laryngopharyngeal Dysesthesia

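### No toxicity limit is stated for the 30-patient expansion, yet Section 11.7 relies on stopping rules and lists dose escalation as a response to excess toxicity

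*Combined protocol and SAP*

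**What the plan says.** Section 3.2 counts DLTs in the first five evaluable patients. With none or one, enrollment may go on to the expansion; with two or more it must not, and other oxaliplatin and capecitabine doses may be considered. Section 3.3 opens the expansion "Once 5 evaluable subjects have been treated in the safety validation cohort with no more than one occurrence of DLT" and sets no later limit. Section 3.1 defines evaluability for DLT only in the Safety Validation Cohort. Section 9.1.2 plans a descriptive summary of adverse events.

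At trial level, the rest is in Section 11.7:

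- Trigger: "If an unexpected frequency of Grade 3 or 4 adverse events occurs, depending on their nature". No expected rate, count or denominator is given.
- Response: "This may require a protocol amendment, dose escalation, or potentially closure of the study".
- A Lead PI duty to ensure that "Stopping rules for toxicity and/or response are met". The qualifier for applicability is attached to the interim-analysis line, not to this one.
- Routine visits after the third subject, "followed by annual monitoring of 1-3 subjects until the study is closed to enrollment". The sentence goes on to cover the time until subjects no longer receive interventions of more than minimal risk.
- "The DCI Safety Oversight Committee (SOC) will perform annual reviews on findings from the DCI Monitoring Team visit", together with safety data from the Principal Investigator.

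The synopsis gives the accrual period: "Estimated duration of subject enrollment is 12 months". On oxaliplatin, the neurotoxicity section (7.2.1.2.1) states: "Dose escalations of oxaliplatin are not permitted at any time".

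**The concern.** Most patients are treated after the only numeric check has been passed, and a check on five patients often lets a toxic regimen through. The expansion also differs from what was checked: a week of pembrolizumab alone, a 28-day first cycle, and external sites.

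The text meant to govern this period has two faults. The Lead PI must ensure that stopping rules are met, but for patients 6 to 35 there are none to meet. And the sentence on excess Grade 3 or 4 events names an action that would increase exposure. At stake is whether accrual would pause in time if the regimen proved too toxic, and whether anyone could later show that it should or should not have paused.

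**Working it through.** The documents give no error rate or boundary for any toxicity rule, so there is no stated figure to reproduce. The true DLT rates p below are assumptions.

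**Inputs.** Safety cohort of 5, proceed with at most 1 DLT (Section 3.2). Expansion of 30 (Section 3.3). Enrollment over 12 months (synopsis). Expansion Cycle 1 of 28 days (Section 3.3).

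**Step 1: the five-patient rule.** P(proceed) = (1−p)^5 + 5p(1−p)^4. At p = 0.40 this is 0.078 + 0.259 = 0.337. One DLT in five, which is a pass, has a one-sided 95% upper limit equal to the 95th percentile of Beta(2, 4), or 66%.

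**Step 2: events in the expansion.** If it opens and all 30 are treated, 30p have a DLT-level event: 12 at p = 0.40. Averaged over trials that never open, the figure is 0.337 × 12 = 4.0.

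**Step 3: scheduled review against accrual.** 35 patients in 12 months is 2.9 a month, so 30 enter in 30 / 2.9 = 10.3 months. This takes accrual as even and ignores the hold after patient 5. About one annual committee review falls within enrollment.

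**Step 4: an example rule.** Count events over all patients, including the first five. Pause at 6 or more of the first 15, or 9 or more of the first 25. Start from the distribution of DLTs in five patients, kept to 0 or 1; add Bin(10, p) and remove totals of 6 or more; add Bin(10, p) again and remove totals of 9 or more. At p = 0.40, given that the expansion opened, the first check pauses 0.321 and the second 0.257, in all 0.577. The probability that the expansion opens and no limit is met is 0.337 × (1 − 0.577) = 0.14.

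| Assumed true rate | 15% | 20% | 30% | 40% | 50% |
|---|---|---|---|---|---|
| P(proceed), Section 3.2 | 84% | 74% | 53% | 34% | 19% |
| Expected events in 30 if opened | 4.5 | 6 | 9 | 12 | 15 |
| P(pause), ≥6/15 or ≥9/25, given opened | 0.8% | 3.5% | 23% | 58% | 86% |
| P(opened and no limit met) | 83% | 71% | 41% | 14% | 3% |
| P(pause), stricter ≥5/15 or ≥8/25 | 3.5% | 11% | 42% | 76% | 94% |

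**Step 5: patients treated, only if every pause becomes closure.** A 28-day window at 2.9 a month lets in 2.7 further patients, taken as 3. At p = 0.40 the mean is 0.321 × 18 + 0.257 × 28 + 0.423 × 35 = 27.8, against 35.

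**The case against.** A reader might infer that Section 11.7 cannot be applied at all, or that the expansion runs without safety oversight. The documents do not support that. Action appropriate to the nature and frequency of events can be taken by judgement, up to closure. The Lead PI tabulates adverse events continuously. Section 11.7 also allows extra monitoring for cause, prompted by unexpectedly frequent serious toxicity and requested by several bodies, including the Safety Oversight Committee and the IRB. Section 10.2 requires SAE reports from external sites within 24 hours and to the supporting company within 2 business days, study-related deaths to the IRB within 24 hours, and FDA reports at 7 or 15 days with alerts to all investigators. Sections 5.7 and 7 protect individual patients. All of this stands, but none of it contains a count that pauses accrual.

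The stopping-rules line does have a referent in Section 3.2, and its and/or wording does not demand a response rule. That is fair for the first five patients. It leaves the duty empty for the next 30.

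The institutional Data and Safety Monitoring Plan and the external-site monitoring addendum are cited but were not supplied. A limit there can be neither confirmed nor excluded.

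Dose escalation is probably a slip for reduction; the synopsis has a similar one where it calls the expansion the Dose Escalation Cohort. Even so, it stands in the sentence on the response to harm. Whether to set a numeric boundary in a 30-patient expansion is a design choice.

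**Conclusion.** The point holds as a defect in the text plus a gap in the plan. Dose escalation is wrong as written, and Section 11.7 relies on stopping rules that the supplied text does not provide after patient 5. What remains for the expansion is oversight by judgement, without a stated limit.

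The gap matters because the earlier rule is weak: an assumed true 40% rate passes it about one time in three, and about 12 of 30 expansion patients would then be expected to have a DLT-level event if nobody intervened. The example rule would lower the chance of opening and never meeting a limit from 34% to 14% at 40%, and from 53% to 41% at 30%.

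It would be tempting to say that such a rule treats 28 patients instead of 35 at a true 40%. That holds only if every pause becomes closure; a pause for review may end with accrual resuming. The figures also assume one event rate across both cohorts, despite their different first cycles and windows.

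**What to change.** 1. In Section 11.7, replace dose escalation with dose reduction of oxaliplatin and capecitabine, or an accrual pause. Section 7.1.1 allows no pembrolizumab reduction.
2. In the stopping-rules line, delete the reference to response and cite Section 3.2 plus an expansion rule stated in Section 3.3. If a limit already exists in the institutional plan, cite that instead.
3. As an example rule, count events of the Section 3.2.1 type over Cycle 1: Days 1-21 in the safety cohort and Days 1-28 in the expansion. With chemotherapy starting on Day 8, a 21-day window would cover only 14 days of the combination. Pause accrual for Safety Oversight Committee review at 6 or more of the first 15 patients or 9 or more of the first 25. The sponsor sets the final limits. The Section 3.2.1 item on delay of Cycle 2 is known only after this window, so the rule should say whether it counts.

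The cost is a few sentences and two checks on adverse events already assessed weekly in Cycle 1, with no extra patients or visits. The downside is a false pause in 0.8% of opened trials at a true 15% and 3.5% at 20%, and low sensitivity at 30% (23%). The stricter limits raise that to 42%, but pause 11% at 20%.
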